6.2. Secondary efficacy endpoints

- 1) Time to TB-IRIS event (from start of ART to onset of IRIS symptoms in days)
- 2) Severity of TB-IRIS events (defined by the following: need for hospitalisation for IRIS, C-reactive protein, neurological involvement)
- 3) Duration of TB-IRIS event (from onset of symptoms/signs to resolution of TB-IRIS symptoms and signs)

- 4) Mortality attributed to TB and TB-IRIS
- 5) All-cause mortality
- 6) Composite endpoint of death, hospitalization, or hepatotoxicity (using the protocol-specified definition of Grade 3 or 4 increase in ALT or bilirubin).
- 7) Other (non-TB) IRIS events
- 8) Quality of life assessment (measured using PROQOL-HIV, EQ-5D-3L, HIV symptom index and Karnofsky score)
- 9) Adverse events and severe adverse events ascribed to TB treatment, ART or co-trimoxazole. This will include a pre-specified analysis of drug-induced liver injury and drug rash. This assessment will include the number of treatment interruptions for drug adverse events.
- 10) Discontinuation of either ART or TB treatment for > 5 days due to adverse events.
- 11) Number of hospitalizations and total days hospitalized

6.3. Secondary safety and tolerability endpoints

- 1) Corticosteroid-associated adverse events, classified by severity and relation to study drug. These will include hypertension, hyperglycaemia, hypomania/mania (diagnosed by psychiatrist), depression (diagnosed by psychiatrist), acne, epigastric pain, upper gastrointestinal bleeding, Cushingoid features, new oedema and avascular bone necrosis.
- 2) Laboratory safety data: glucose, full blood count and electrolytes
- 3) Other infections (AIDS-related, bacterial, fungal and viral) and malignancies (Kaposi's sarcoma)
- 4) All grade 1, 2, 3 and 4 adverse events (clinical and laboratory using the ACTG grading system)

6.4. Quality of Life (QoL) assessments

As a secondary outcome measure we will perform health-related quality of life measures of the participants included in the trial at week 0, 4 and 12. The following measurements will be performed: PROQOL-HIV, EQ-5D-3L, HIV symptom index and Karnofsky score. See section 21 for details of this QoL substudy.

7. Study medication

7.1. Prednisone and identical placebo

Study medication will be prednisone tablets (5mg) or identical placebo tablets. The study medication will be prepared by the Gulf Drug Company, Durban, South Africa. This generic pharmaceutical company supplies prednisone to the government hospital pharmacies in South Africa (marketed as Trolic 5mg tablets). They manufactured prednisone and placebo tablets for our previous trial of prednisone for TB-IRIS treatment. We have estimated a requirement of 21 000 placebo tablets and 21 000 prednisone tablets.

Participants will receive 40mg (8 tablets) daily of 5mg prednisone (or identical placebo) for 14 days followed immediately by 20mg daily (4 tablets) daily of 5mg prednisone (or identical placebo) for 14 days. Participants will start the study medication on the same day or within

48 hours of initiating antiretroviral therapy. The total duration of study medication will be 28 days.

7.2. Manufacture and delivery of study medication

The study medication will be manufactured by the Gulf Drug Company in Durban. The University of Cape Town will be charged for the manufacture of the study medication and a quote has been obtained. The Gulf Drug Company will deliver the medication to the Grootte Schuur Hospital pharmacy (an independent pharmacy) as one container of prednisone and one container of placebo. The Grootte Schuur Hospital pharmacist will sign for receipt of the medication.

7.3. Packaging of study medication

The randomization sequence for the trial will be generated by an independent statistician according to a blocked (block size 8), 1:1 randomisation sequence. This will be sent to the independent pharmacist at Grootte Schuur Hospital. This pharmacist will pack the prednisone and placebo tablets into sequentially labeled medicine containers labeled from participant 1 to 240. There will be two medicine packages for each participant:

- 1) **Day 0-14:** 8 x 14 tablets = 112 tablets
- 2) **Day 15-28:** 4 x 14 tablets = 56 tablets

This process will be undertaken independent of any investigators or study team members who will remain blinded with respect the randomization sequence and the packaging of the study medication. Once all the study medication has been packaged it will be transferred to the clinical trial site pharmacy and the on-site pharmacist will sign for receipt of the study medication.

7.4. Storage at the clinic

The study medication will be stored in the clinic research pharmacy which is locked by the pharmacist on site when she is not present. It will be stored at room temperature (at or below 25 degrees Celsius in adherence with manufacturers' instructions) and a temperature log will be kept in the pharmacy. Study drug management and accountability will be described in a specific SOP.

7.5. Dispensing of medication

Medication will be dispensed according to patient enrollment number by the study pharmacist from patient 1 to 240. The pharmacist will keep a log of all study medication dispensed recording date, patient number and initials and packet number.

Study medication will be dispensed on two occasions:

At Week 0 visit, the first 14 days medications will be dispensed

At Week 2 visit, the 15-28 days medication will be dispensed

At the week 1, 2 and 4 visit participants' adherence to study medication will be checked by means of pill counts and the number of tablets returned will be recorded on the CRF. Participants will be asked to bring back their medication packet for this purpose.

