10.1. Schedule of events

| Study visit | Screening | Enrollment | Entry Week 0 | Week 1 | Week 2 | Week 4 | Week 8 | Week 12 | Un-scheduled visit |
|-----------------------------|---------------|-----------------|--------------|---------|----------|----------|----------|----------|--------------------|
| ART day | Not specified | Aim for -7 to 0 | 0-2 | 7 +/- 4 | 14 +/- 4 | 28 +/- 4 | 56 +/- 4 | 84 +/- 7 | Not specified |
| Document HIV status | X | | | | | | | | |
| Assess eligibility criteria | X | X | X | | | | | | |
| Screening ICF | X | | | | | | | | |
| Enrollment ICF | | X | | | | | | | |
| Study drug administration | | | X | | X | | | | |
| Past medical history | X | | | | | | | | |
| Current symptoms | X | X | X | X | X | X | X | X | X |
| IRIS questions | | | | X | X | X | X | X | X |

| | | | | | | | | | |
|--------------------------------------|---|---|---|---|---|---|---|---|-----------------|
| Adverse events assessment | X | X | X | X | X | X | X | X | X |
| Medication review | X | I | X | X | X | X | X | X | X |
| Karnofsky score | X | | X | X | X | X | X | X | X |
| Pill count | | | | X | X | X | | | |
| QOL assessments | | | X | | | X | | X | |
| Examination | X | I | X | X | X | X | X | X | X |
| Na,K,Cr,glucose | X | I | X | | X | X | | X | I |
| ALT, Alk Phos | X | I | X | | X | X | | X | I |
| FBC, diff | X | I | X | | X | X | | X | I |
| CRP | | I | X | | X | X | | X | I |
| CD4, HIV viral load | X | | | | | | | X | |
| HepBsAg | X | | | | | | | | |
| Serum CrAg | X | | | | | | | | |
| Urinary pregnancy test | X | I | I | I | I | I | I | I | I |
| Storage bloods and immunology assays | | | X | | X | X | | X | If IRIS suspect |
| Storage urine | | | X | | | | | X | If IRIS suspect |
| MTB/RIF Xpert, culture and DST | X | | | | | X | | X | |
| Initiate ART | | | X | | | | | | |

I = If clinically indicated

ICF = Informed consent form

Study visits will occur at screening for the study, at an enrollment visit, week 0 (the day the patient starts study drug), week 1, week 2, week 4, week 8 and week 12. A window period of +/- 4 days will be allowed for all visits apart from the week 0 visit (no window) and week 12 (where a window of +/- 7 days will be allowed). If visits do not occur in these windows then a “missed visit” will be recorded.

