Patients will be telephoned before each visit by the nurse or counselor to remind them of the visit. Patients will be re-imbursed R150 for each scheduled visit towards transport and meal costs. Patients who are screened but not recruited will also be re-imbursed for this visit. This will be stated in the informed consent forms. If patients are lost to follow up then an attempt to ascertain their outcome at 12 weeks will be made telephonically. At each study visit the research team will check that the patient has sufficient supply of TB medication (or is receiving daily from TB clinic) and ART and other prescribed medication.

A maximum of 40ml blood will be drawn at any study visit. Only trained personnel will perform phlebotomy. Patients who have symptomatic anaemia (Hb<8g/dL with symptoms attributable to anaemia) will not have more than 30ml of blood drawn at any given visit.

Screening visit

Patients identified in the HIV-TB clinic (or referred there specifically for screening for this study, as mentioned in 3.8) who potentially meet enrollment criteria will be referred to the study team. Patients should have been on TB treatment for ≤ 21 days at this screening visit. Patients will be briefly informed about the study and written informed consent will be taken from the patient to screen them for eligibility for the clinical trial with a screening visit informed consent form. If patients sign screening consent they will be assessed with the inclusion and exclusion criteria for the trial. The HIV status of the patient will also be documented by the study team at this visit. In all patients being screened for the trial, regardless of whether they have had a previous positive HIV test, HIV testing will be performed with appropriate counseling using two different rapid HIV tests. This is the standard of care in the clinic. If the results are discrepant or indeterminate blood will be sent to the National Health Laboratory Services laboratory for ELISA confirmation. In addition, as stated below an HIV viral load is performed at this visit, that will serve as confirmatory of the HIV diagnosis. The following study procedures will be performed (blood and urine will only be taken if patients fulfill inclusion criteria and have no exclusion criteria after notes review, history and examination):

- 1) Past medical history
- 2) Current drugs and drug allergies
- 3) Current symptoms
- 4) Physical examination

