- 5) Full blood count and differential
- 6) C-reactive protein (CRP)
- 7) Bloods for immunological assays
- 8) Chest radiograph (for all participants)
- 9) Quality of life assessments
- 10) Karnofsky score
- 11) Assess adverse events
- 12) Issue Day 1-14 study medication

A randomization number (corresponding to the next sequential study medication container) will be assigned at this visit and documented on the enrollment log.

Week 1 visit (Day 7 +/- 4 days)

- 1) Current symptoms and specific TB-IRIS symptom screen
- 2) Physical examination
- 3) ART and study drug pill count to assess adherence

Week 2 visit (Day 14 +/- 4 days)

- 1) Current symptoms and specific TB-IRIS symptom screen
- 2) Physical examination
- 3) Na, K, creatinine, glucose
- 4) ALT, alkaline phosphatase
- 5) Full blood count and differential
- 6) C-reactive protein (CRP)
- 7) Bloods for immunological assays
- 8) ART and study drug pill count to assess adherence
- 9) Karnofsky score
- 10) Assess adverse events
- 11) Issue Day 15-28 study medication

Week 4 visit (Day 28 +/- 4 days)

- 1) Current symptoms and specific TB-IRIS symptom screen
- 2) Physical examination
- 3) Na, K, creatinine, glucose
- 4) ALT, alkaline phosphatase
- 5) Full blood count and differential
- 6) C-reactive protein (CRP)
- 7) Bloods for immunological assays
- 8) ART and study drug pill count to assess adherence
- 9) Sputum for MTB/RIF Xpert, culture and DST (to assess the effect of corticosteroids on sputum conversion)
- 10) Quality of life assessments
- 11) Karnofsky score
- 12) Assess adverse events

Week 8 visit (Day 56 +/- 4 days)

- 1) Current symptoms and specific TB-IRIS symptom screen

- 2) Physical examination
- 3) ART and study drug pill count to assess adherence
- 4) Karnofsky score
- 5) Assess adverse events

Week 12 visit (Day 84 +/- 7 days)

- 1) Current symptoms and specific TB-IRIS symptom screen
- 2) Physical examination
- 3) Na, K, creatinine, glucose
- 4) ALT, alkaline phosphatase
- 5) Full blood count and differential
- 6) C-reactive protein (CRP)
- 7) CD4 and HIV viral load
- 8) Bloods for immunological assays
- 9) ART and study drug pill count to assess adherence
- 10) Sputum for MTB/RIF Xpert, culture and DST (to assess the effect of corticosteroids on sputum conversion)
- 11) Quality of life assessments
- 12) Karnofsky score
- 13) Assess adverse events
- 14) Refer back to HIV-TB clinical service if clinically stable

Unscheduled visits/sick visits

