13.9. Interruptions in study drug (by the participant)

If the participant interrupts the study drug then a discussion will occur regarding how long the interruption was for and the reasons the patient had for the interruption. If the patient interrupted because of side effects and does not want to restart then they will not be restarted and this will be documented. If the participant is agreeable to restarting study medication, then study medication will be restarted if the interruption was 5 days or less. If it was more than 5 days study medication will not be restarted. All interruptions will be fully documented.

In all cases participant follow-up will occur to week 12 unless consent for the trial is withdrawn by the participant.

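### Pack 1 holds exactly 14 doses, but pack 2 may be issued as late as day 18, so the dispensing and visit-window rules permit a short break in study drug that section 7.1 does not allow (minor).

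*Supplement*

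**What the plan says.** All references are to protocol version 1.4.

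- **Dosing (7.1).** After 14 days at 40 mg, treatment is "followed immediately by 20mg daily (4 tablets) daily" for a further 14 days.
- **Packaging (7.3).** Each participant has two containers. The first holds "8 x 14 tablets = 112 tablets", the second 56 tablets.
- **Dispensing (7.5).** There are two dispensing occasions: the first pack at Week 0, and then "At Week 2 visit, the 15-28 days medication will be dispensed". The Week 2 procedure list in 10.1 repeats this: "Issue Day 15-28 study medication".
- **Visit window (10.1).** "A window period of +/- 4 days will be allowed for all visits apart from the week 0 visit (no window") and Week 12. Week 2 is day 14 ± 4, so days 10 to 18 are in window, and only a visit outside the window is recorded as missed.
- **Related provisions.** Section 10.1 also says "Patients will be telephoned before each visit by the nurse or counselor to remind them of the visit". Section 7.5 has a pill count at Week 1. Under 13.9, "study medication will be restarted if the interruption was 5 days or less". Section 7.4 adds: "Study drug management and accountability will be described in a specific SOP". That SOP is not among the documents shown.

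**The concern.** The upper half of the Week 2 window falls after pack 1 is empty. A participant who attends then has complied with the visit schedule and taken every tablet supplied, but has had days without drug that 7.1 does not intend. The planned step from 40 mg to 20 mg becomes 40 mg, nothing, then 20 mg.

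The timing is awkward. Section 3.2 cites a median TB-IRIS onset of 14 days (IQR 7-25), so the break falls soon after the middle of the risk period. Only the prednisone arm loses active drug, so any effect on the primary endpoint would shrink the difference between arms.

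The routine checks would not flag it. No missed visit is recorded, and a participant who has finished pack 1 returns no tablets, so the Week 2 pill count looks perfect. If pack 2 starts on day 18, only 10 or 11 of its 14 doses can have been taken by day 28. The protocol specifies both 14 + 14 doses and a 28-day duration, and does not say which prevails after a supply gap. The delayed doses may therefore be recovered or not.

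**Working it through.** **Inputs.** Pack contents (7.3); pack 2 issued at Week 2 (7.5, 10.1); Week 2 on day 14 ± 4 (10.1). There are three readings of the first dose day:
- day 0, because the text of 10.1 makes Week 0 the day study drug starts;
- day 1, from the Day 1-14 label on the first issue in the Week 0 list;
- ART day 2, because the schedule table counts ART days and study drug may start up to 48 hours after ART.

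**Pack contents reproduced.** 8 × 14 = 112 and 4 × 14 = 56 tablets, so 168 per participant.

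**No spare stock.** Section 7.1 orders 21 000 tablets per arm. The need is 120 × 168 = 20 160. The surplus is 840, or 840 / 120 = 7 tablets per participant. That is less than one 8-tablet dose, and none of it is in the participant packs.

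**Gap formula.** Last pack 1 dose day = start day + 13. Gap = max(0, first pack 2 dose day − last pack 1 dose day − 1). The first pack 2 dose is taken on the visit day or the day after.

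| Reading | Last pack 1 dose | Visit day 14 | 15 | 16 | 17 | 18 |
|---|---|---|---|---|---|---|
| Day-0 start, dose on visit day | 13 | 0 | 1 | 2 | 3 | 4 |
| Day-0 start, dose next day | 13 | 1 | 2 | 3 | 4 | 5 |
| Day-1 start, dose on visit day | 14 | 0 | 0 | 1 | 2 | 3 |
| Day-1 start, dose next day | 14 | 0 | 1 | 2 | 3 | 4 |
| ART-day-2 start, dose on visit day | 15 | 0 | 0 | 0 | 1 | 2 |
| ART-day-2 start, dose next day | 15 | 0 | 0 | 1 | 2 | 3 |

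Visits on days 10-13 give no gap on any reading, and day 14 gives none on all but one. At day 18 every reading has a gap, from 2 to 5 doses.

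**Amount of drug.** The course is 14 × 40 + 14 × 20 = 840 mg. A 4-dose gap delays 4 × 20 = 80 mg (9.5%). Gaps of 2 and 5 doses delay 40 mg (4.8%) and 100 mg (11.9%).

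**Against the stopping rule.** Section 13.10 stops study drug after an interruption of more than 5 days. The longest gap is 5, so none ends treatment.

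**The case against.** The strongest reply is that 7.1 is itself a written rule, and that the window in 10.1 decides only whether a visit counts as missed. Read together, the site should issue pack 2 before pack 1 runs out, and days 10-14 already allow that. This stands in part. It would be wrong to infer that a late attender has satisfied every rule, because the gap breaches 7.1. The right description is an inconsistency: the window is looser than the dosing rule, and nothing in 7.5 or 10.1 tells the site to use only its first part.

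Existing provisions also help. Reminder calls make late attendance less likely. The Week 1 pill count (days 3-11) lets staff see when pack 1 will run out. Section 13.9 tolerates the gap, although it is written for interruptions by the participant and supplies no tablets. The SOP may contain a booking rule, and booking Week 2 by day 14 would be consistent with 7.5. These reduce or tolerate the gap, but nothing shown removes it.

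It is also fair that 4 doses is not the only headline. On the Day 1-14 and Day 15-28 labels, with a dose on the visit day, the maximum is 3.

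Lastly, the rules apply alike to both blinded arms and the primary analysis is intention-to-treat (14.2.2; SAP section 3), so no analysis is invalidated. That is correct, and it is why the point is minor.

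**Conclusion.** The inconsistency is real and the severity is minor. Sections 7.1, 7.3, 7.5 and 10.1 cannot all be met for an adherent participant seen late in the Week 2 window. At day 18 the break is 4 doses with a day-0 start, 3 on the Day 1-14 label, and 2 to 5 across readings. These figures assume only that every pack 1 tablet is taken as directed and that no drug comes from elsewhere.

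A reader might infer a measurable dilution of the primary result. The documents do not support a figure. As an illustration, assume that a quarter of onsets is spread evenly between the cited median and upper quartile, 25% / 11 days = 2.27% per day, and that the whole design effect (35% v 17.5%) is lost on gap days. A 4-dose gap then costs 4 × 2.27% × 17.5 = 1.6 percentage points in those affected. If 10% to 50% of the prednisone arm had that gap, the cost across the arm is 0.16 to 0.80 points. This is not an upper bound. The share affected is invented, because no visit-day distribution is given. Onsets may also be denser near day 14: the quarter between days 7 and 14 implies 25% / 7 = 3.6% per day. What can be said is that only late attenders are affected, treatment can resume in every case, and any bias is towards no effect.

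**What to change.** Amend 7.5 and 10.1 so that the Week 2 dispensing visit is booked for days 10-14, preferably no later than the last pack 1 dose. The Week 1 pill count can confirm that date. Keep ±4 days for the Week 2 assessments, so that a later attender is still not recorded as a missed visit.

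This needs no extra tablets, visits or staff, and it keeps the Week 2 clinical review ahead of the second supply. The cost is a slightly tighter booking day. It does not help anyone who still comes after day 14, and the one-dose gap on day 14 remains if dosing started on day 0 and the visit-day dose is not taken.

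Handing over pack 2 at Week 1 would close more of the gap, but I would not recommend it. It supplies the second fortnight of steroid before the Week 2 symptom review, examination and adverse event check, in patients for whom 3.8 acknowledges possible harm. It also leaves them holding two packs of the same tablets with different daily counts.

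The SAP reports that all 240 participants have been enrolled. For this trial, the dated dispensing log required by 7.5 can show how often a gap could have arisen. The wording change would serve the larger trial that 3.1 foresees.

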7.6. Maintenance of randomization concealment

Participants, clinical site staff, investigators, data management personnel and the study statistician will remain blinded to the treatment allocation throughout the course of the trial. The randomization sequence will be kept away from the trial site securely by the independent statistician. This statistician will store an electronic copy and a hard copy. A printed and sealed copy of this randomization sequence will also be given to the Sponsor representative (Deputy Dean of Research, Faculty of Health Sciences) for storage to ensure a back-up copy is available. At the trial site the placebo and prednisone tablets and packaging will be identical with no markings or labeling to differentiate which medication containers contain prednisone or placebo. Only once the trial database is locked will the randomization sequence be made available to the trial team.

In the event of unblinding of an individual participant being required in the opinion of the attending clinician (see section 13.10.) the independent statistician will be contacted for this information. In order that unblinding could occur if the independent statistician was unavailable, a set of sealed opaque numbered envelopes with the random allocation assignment of each participant in will be kept at the Groote Schuur Hospital pharmacy in a locked box. It will be visible when an envelope has been opened and this will be checked by the external study monitor.

7.7. Expiration and re-ordering of medication

The expiration date of the study medication will be noted upon delivery. It is planned that the product will have a shelf life that covers the entire study duration. The manufacturers have confirmed a shelf-life of 24 months for prednisone. This will be specified in the order. However, we will have a plan to cover the contingency that product reaches its expiry date. Six months prior to the expiration date, additional prednisone and placebo tablets will be ordered from the Gulf Drug Company. The same process will be followed with respect to delivery, blinding procedures, packaging and storage.

